#### **1.** Rationale for the study

Preliminary data in the development of a new hsRDT indicated that this hsRDT has a significantly higher sensitivity than cRDT and will perform better in detecting low density malaria infections (Personal communication; [name], Bill and Melinda Gates Foundation), and we anticipate that it may play a critical role in reactive case detection strategy. The current tools such as microscopy or cRDT are insufficient in identifying these infections and missing them may pose a great drawback for the progress of preparation for malaria elimination. In addition to its high sensitivity, hsRDT is a point of care test, therefore it is convenient for large scale testing and sustainable in resource-limited settings. This tool is urgently needed in the current surveillance activities in Myanmar during the time of preparation for the pre-elimination and subsequent elimination phase. Findings from the proposed study will also contribute useful data in the development of national standard operating procedures for ACD with potential value of the new hsRDTs as a screening tool in the RCD strategy.

#### 3.3. Potential Risks and Benefits

## 3.3.1. Potential risks

**Effects of finger sticks**. Very small risks of bruising, bleeding, infection and fainting can accompany these procedures. Study-related blood collection for malaria diagnostic testing (blood smear on microscope slides or rapid diagnostic test) and dried blood spot sample can be accomplished by using finger-stick.

**Potential risks to study personnel**. The main risks to study personnel are from accidental exposure to blood and body fluid borne infections. SOPs for staff safety are

used in clinical and laboratory areas, including sharps management, hazardous waste management, etc. Universal precautions are used for handling all body fluids.

Because the described analyses pose minimal appreciable additional risks to the trial participants but present potential benefits to their communities and others living in malaria endemic areas, the risk-to-benefit ratio is very low.

#### 3.3.2. Known potential benefits

Participants may not receive any direct benefit from their participation in the study. However, if symptoms of other illnesses are noted, participants will be referred for evaluation and treatment at the appropriate local clinic.

If malaria parasites were identified by cRDT or hsRDT, participants will receive appropriate anti-malaria treatment promptly and potential transmission will be interrupted, benefiting the community. The benefits to the community could include improved tools for surveillance and diagnosis of malaria. Results from this study may help malaria control programs improve understanding the degree and distribution of "silent" reservoir that cannot be readily detected using current diagnostic tests.

# 4. Study objectives

**General objective:** To evaluate the performance of the highly-sensitive rapid diagnostic test (hsRDT), developed by SD Bioline, versus conventional RDT (cRDT), compared with PCR as the gold standard, in reactive case detection to identify additional malaria infections in Rakhine State, Myanmar

#### **Specific objectives:**

1. To evaluate the prevalence of malaria infections identified by the new hsRDT in comparison with that detected by cRDT and PCR

Outcomes: malaria test positivity rate by cRDT, hsRDT and PCR, respectively

2. To assess the diagnostic performance characteristics of hsRDT *versus* cRDT, using PCR as gold standard, in the detection of *P.falciparum* infections

Outcomes: Sensitivity, specificity, positive and negative predictive values of hsRDT and cRDT

3. To evaluate correlation of detection capability between cRDT and hsRDT

Outcomes: Correlation of test positivity rate by the three different study tests

4. To identify risk factors associated with malaria infection, including but not limited to, socio-demographic factors and travel history related with malaria index cases

Outcome: Relative risk of malaria in association with different risk factors identified

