# 5. Methodology

# 5.1. Study Design & Overview

This is a prospective community-based single-center reactive case detection (RCD) study to assess the performance of hsRDT versus cRDT in identifying individuals with malaria infection ("Secondary case") in a population living and/or working in a close physical proximity to an "index case."

"Index case" is defined as a malaria infection identified by passive surveillance by local health services (rural health center, sub-centers) or village malaria workers (VMWs), by cRDT or microscopy.

"Secondary case" is defined as any malaria infection identified by any of the study diagnostic test: cRDT, hsRDT or PCR, regardless of the presence of acute clinical illness. The secondary cases will be identified actively and systematically around the residence, or work place if relevant, of the index case.

The study will be initiated after obtaining administrative (Myanmar MoHS, NMCP, PMI) and ethical approval (Myanmar DMR ERC, CDC IRB and UMB IRB) from all relevant institutions. Consent, and assent and adult permission when appropriate, will be sought for all index cases and secondary cases. Only those who are eligible and provide informed consent will be enrolled in the study.

All index cases parasitologically confirmed by cRDT or microscopy will be appropriately and promptly notified to the study team, using mobile phone technology where possible, to ensure timely enrollment. The home of the index case, or work place when relevant, will be visited within three days of the diagnosis, and s/he will be interviewed with a standardized case investigation form. During the visit, all members of the index case household and all members of the nearest 10 households, aged 5 years or above, will be invited to participate in the study. All participants in the study will be interviewed with a structured questionnaire, tested with cRDT and hsRDT, and a dried blood spot (DBS) will be collected for subsequent PCR analysis. All cases parasitologically confirmed by cRDT or hsRDT will be appropriately treated, following the national treatment guideline. DBS samples will be collected, processed and stored until analysis following the World Wide Antimalarial Resistance (WWARN) Molecular Testing for Malaria Standard Operating Procedures DBS Sample Collection and Transportation (http://www.wwarn.org/learning/procedures/dbs-sample-collection-andtransportation).

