The prevalence of secondary malaria cases (number positive /number tested), by cRDT and hsRDT will be compared, using PCR as gold standard. Using simple analysis of performance characteristics, the sensitivity and specificity of hsRDT will be estimated in the study population. Potential correlation between the detection rate by cRDT, hsRDT and PCR will be assessed.

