# 7. Statistical consideration and Data Management

## 7.1. Power calculation with available sample size

The primary limitation is the size of population that needs to be screened since malaria burden may be low in the study sites, and associated financial costs and logistical difficulties.

The primary endpoint of this proposed study is the prevalence of secondary malaria cases identified by hsRDT in comparison with usPCR prevalence. Based on our current data on prevalence of *P. falcipaum* in 2016, and logistical and financial considerations, the recruitment of 50 index cases is feasible in a given study period. This will give us a total of 1980 individuals for testing of secondary cases in ACD, assuming the average household member of 4.5, 11 households for each index case (counting the household of the index case) and a refusal rate of 20% (4.5 persons/HH x 11 HH x 50 index cases x 0.80=1980).

We conservatively estimate that hsRDT will detect 20% of usPCR+ *P. falciparum* infections (i.e., sensitivity of hsRDT=0.2 using usPCR as gold standard). We expect very few recently treated individuals to be enrolled in the study, so that hsRDT should only rarely give a positive result when usPCR does not. Hence we assume that the specificity of hsRDT is 0.995. Table 1 shows estimated statistical power that can be achieved with the proposed sample size of 1980 for comparing the prevalence by hsRDT and the prevalence by usPCR, at different malaria prevalence by usPCR and different sensitivity of hsRDT, using a two-sided McNemar test with a Type I error of 5%. (PASS version 11. NCSS, LLC. Kaysville, Utah, USA)

As shown in Table 1, if the sensitivity of hsRDT is 0.2 and the specificity of hsRDT is 0.995, a sample size of 1980 subjects achieves at least 92% power to detect the difference in prevalence between hsRDT and usPCR when the malaria prevalence is 2% or higher. If the sensitivity of hsRDT is 0.5 (see the last four columns of Table 1), a sample size of 1980 subjects achieves at least 86% power when the malaria prevalence is 3% or higher. If the prevalence of malaria is higher, the performance of hsRDT will be better with a higher sensitivity and positive predictive value.

 Table 1. Statistical power expected with proposed sample size of 1980 at different malaria

| prevalence and different sensitivity of hsRDT (assumed sensitivity of 20% or 50% and |
|--|
| specificity 99.5%)   |

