# 7.2. Analytical Plan

All data will be double-entered into Epi-Info and any discrepancies will be reviewed against the paper forms. All analyses will be conducted using Stata/SE (version 14), using data from the participant interviews and the three parasitological tests.

The malaria test positivity rate will be calculated as a proportion of samples tested that are positive using cRDT, hsRDT and PCR, respectively. Corresponding 95% confidence intervals (CIs) will be computed using exact method. A 2x2 table method will be used to calculate the sensitivity, specificity, positive and negative predictive values of hsRDT (and cRDT) and their corresponding 95% CIs using PCR as gold standard. The malaria prevalence by each test (e.g., the rate of malaria test positive) will be compared between each two tests (hsRDT vs PCR; cRDT vs PCR; hsRDT vs cRDT) using McNemar test. All statistical tests will be performed with a two-sided significance level of 0.05.

Descriptive analysis will be conducted to assess socio-demographics characteristics. Univariate analysis will include t-test and non-parametric methods for continuous variables and chi-square test for comparison of categorical variables. Multi-level regression models will be developed to examine risk factors significantly associated with malaria infections, accounting for clustering by index case.

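### Objective 3's only outcome, a correlation of test positivity rates, does not measure whether cRDT and hsRDT identify the same people

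*Combined protocol and SAP*

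**What the plan says.** Objective 3, in the Protocol Summary and again in section 4, is "To evaluate correlation of detection capability between cRDT and hsRDT". The one outcome listed under it is "Correlation of test positivity rate by the three different study tests". Section 5.1 restates this as "Potential correlation between the detection rate by cRDT, hsRDT and PCR will be assessed". The aim names two tests and the outcome names three.

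Section 7.2 defines the quantity to be correlated: "The malaria test positivity rate will be calculated as a proportion of samples tested that are positive using cRDT, hsRDT and PCR, respectively". It then gives two analyses that bear on how the tests compare:

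- Prevalence by each test "will be compared between each two tests (hsRDT vs PCR; cRDT vs PCR; hsRDT vs cRDT) using McNemar test".
- Sensitivity, specificity and predictive values of each RDT, with PCR as the reference.

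Section 7.2 names no correlation coefficient, no unit over which a correlation would be taken, and no agreement statistic. The design is paired. Section 5.1 says "All participants in the study will be interviewed with a structured questionnaire, tested with cRDT and hsRDT", and a dried blood spot is taken for PCR.

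**The concern.** A positivity rate belongs to a group. Three tests in one study population give three numbers, and three numbers have no correlation. To calculate one, the analyst would have to choose a unit, such as the index-case cluster or the village, and the plan names neither. Across such groups, two tests that both respond to infection will have correlated rates wherever prevalence differs between groups, whether or not they pick out the same individuals.

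A programme that must decide what hsRDT adds to cRDT needs the person-level cells: infections found by both tests, by hsRDT only, and by cRDT only. The outcome listed for objective 3 reports none of these.

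**Working it through.** **Stated figures.** The documents give no number for objective 3. The sample size in section 7.1 is "4.5 persons/HH x 11 HH x 50 index cases x 0.80=1980", which reproduces: 4.5 × 11 × 50 × 0.80 = 1980. That is 1980 / 50 = 39.6, or about 40 people per index-case cluster.

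**Step 1: what the planned rates and McNemar test can show about agreement.** Take N = 1980 and, for illustration, 40 positives on each test (40/1980 = 2.02%). Let a be the number positive on both tests, b and c the two discordant counts, and d the number negative on both.

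- Observed agreement: po = (a + d)/N
- Chance agreement: pe = (40/1980)² + (1940/1980)² = 0.9604
- Kappa = (po − pe)/(1 − pe)
- Positive agreement = 2a/(2a + b + c)

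| a | b = c | d | Rate, each test | Exact McNemar p | Overall agreement | Positive agreement | Kappa |
|---|---|---|---|---|---|---|---|
| 0 | 40 | 1900 | 2.02% | 1.0 | 96.0% | 0% | −0.02 |
| 10 | 30 | 1910 | 2.02% | 1.0 | 97.0% | 25% | 0.23 |
| 30 | 10 | 1930 | 2.02% | 1.0 | 99.0% | 75% | 0.74 |
| 40 | 0 | 1940 | 2.02% | 1.0 | 100% | 100% | 1.00 |

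The rates and the McNemar result are the same in all four rows, while agreement runs from none to complete. Overall agreement is no substitute for positive agreement: it is 96% with no shared positive at all.

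**Step 2: expected person-level agreement.** Assumptions not in the documents: cRDT sensitivity 0.3, hsRDT sensitivity 0.5, and the same specificity for both tests. Section 7.1 does use 0.5 as one hsRDT scenario and 0.995 as hsRDT specificity. False positives are taken as independent throughout.

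At prevalence 6%:
- cRDT rate = 0.06 × 0.3 + 0.94 × 0.005 = 0.0227
- hsRDT rate = 0.06 × 0.5 + 0.94 × 0.005 = 0.0347
- pe = 0.0227 × 0.0347 + 0.9773 × 0.9653 = 0.9442
- Independent given infection: both positive = 0.06 × 0.15 + 0.94 × 0.005² = 0.00902. Then po = 1 − (0.0574 − 2 × 0.00902) = 0.9606 and kappa = 0.0165/0.0558 = 0.295.
- Nested (every infection cRDT finds, hsRDT also finds): both positive = 0.06 × 0.3 + 0.94 × 0.005² = 0.01802. Then po = 0.9786 and kappa = 0.0345/0.0558 = 0.618.

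The same steps at prevalence 3% give kappa 0.256 (independent) and 0.528 (nested).

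**Step 3: the cluster-level correlation beside it.** Simulation of 50 clusters of 40, 1,000 runs per setting. Cluster prevalence is gamma-distributed (shape 1 or 2 with mean 6%; shape 1 with mean 3%). Values are ranges of means over settings.

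| Sensitivity, cRDT / hsRDT | Errors in infected people | Correlation of cluster rates | Kappa |
|---|---|---|---|
| 0.3 / 0.5 | independent | 0.42–0.58 | 0.25–0.29 |
| 0.3 / 0.5 | nested | 0.62–0.77 | 0.52–0.62 |
| 0.1 / 0.2 | independent | 0.12–0.22 | 0.06–0.08 |

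The correlation exceeds kappa in every row, because it also picks up variation in prevalence between clusters. It is not a measure of agreement, although in these settings it rises and falls with agreement.

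**The case against.** The strongest reply is that section 7.2 already contains a person-level hsRDT-cRDT comparison. McNemar's test is built on the discordant cells and needs the paired table, and the sensitivities against PCR show which test finds more infections. This stands to a large extent: it would be wrong to infer that the plan ignores paired data or cannot show a difference in yield. What remains, as Step 1 shows, is that equal margins say nothing about overlap, and two accuracy figures against PCR do not say whether the same infected people were found.

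A second reply is that the plan does not commit to a cluster-level correlation. It leaves coefficient and unit open, and a person-level phi coefficient is one possible reading of the aim. That is fair, and the cluster analysis above is one reading of an undefined outcome. But both statements of the outcome speak of a rate, and no phi coefficient is named.

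A third reply concerns size. A reader might infer that the correlation could look reassuring while the tests mostly disagree. The documents do not support this under plausible settings. With independent errors the correlation is only moderate, and it broadly follows kappa. Independence is itself doubtful: section 3.1 says both tests detect HRP2, with detection limits of about 80 against 800–1000 pg/mL, which makes near-nesting more natural. Correlations above 0.8 with no shared positives appeared only when non-overlap was forced and cases were concentrated in 20% of groups at 13%, the rest at 0%. That is a mathematical bound and not a forecast.

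**Conclusion.** The point holds as a minor one. The outcome listed for objective 3 cannot be calculated over the whole study. Taken across clusters or villages, it partly reflects prevalence and does not measure whether cRDT and hsRDT identify the same people, and no other planned analysis quantifies that agreement. The sizes in Steps 2 and 3 rest on an assumed cRDT sensitivity, an assumed overlap between the tests and an assumed spread of prevalence, none of which the documents give.

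The point does not extend to a claim that the correlation would mislead in practice. The primary endpoint in section 7.1 is the hsRDT-usPCR prevalence comparison, no decision rule uses objective 3, and the separate rates, sensitivities and McNemar results would be reported alongside it.

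**What to change.** Replace the objective 3 outcome with person-level paired agreement between hsRDT and cRDT, and likewise for each RDT with PCR if the three-test wording is kept. Report:

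- the cross-classified table already needed for McNemar's test;
- positive and negative percent agreement;
- kappa, with a note that it depends on prevalence;
- confidence intervals that allow for clustering by index case.

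Do not rely on overall agreement. Under objective 2, add the paired hsRDT-cRDT difference in sensitivity among PCR-positive participants.

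The cost is a few lines in the Protocol Summary objectives and in sections 4, 5.1 and 7.2. All three tests are already planned for every participant, so no new data are needed.

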# 5. Methodology

# 5.1. Study Design & Overview

This is a prospective community-based single-center reactive case detection (RCD) study to assess the performance of hsRDT versus cRDT in identifying individuals with malaria infection ("Secondary case") in a population living and/or working in a close physical proximity to an "index case."

"Index case" is defined as a malaria infection identified by passive surveillance by local health services (rural health center, sub-centers) or village malaria workers (VMWs), by cRDT or microscopy.

"Secondary case" is defined as any malaria infection identified by any of the study diagnostic test: cRDT, hsRDT or PCR, regardless of the presence of acute clinical illness. The secondary cases will be identified actively and systematically around the residence, or work place if relevant, of the index case.

The study will be initiated after obtaining administrative (Myanmar MoHS, NMCP, PMI) and ethical approval (Myanmar DMR ERC, CDC IRB and UMB IRB) from all relevant institutions. Consent, and assent and adult permission when appropriate, will be sought for all index cases and secondary cases. Only those who are eligible and provide informed consent will be enrolled in the study.

All index cases parasitologically confirmed by cRDT or microscopy will be appropriately and promptly notified to the study team, using mobile phone technology where possible, to ensure timely enrollment. The home of the index case, or work place when relevant, will be visited within three days of the diagnosis, and s/he will be interviewed with a standardized case investigation form. During the visit, all members of the index case household and all members of the nearest 10 households, aged 5 years or above, will be invited to participate in the study. All participants in the study will be interviewed with a structured questionnaire, tested with cRDT and hsRDT, and a dried blood spot (DBS) will be collected for subsequent PCR analysis. All cases parasitologically confirmed by cRDT or hsRDT will be appropriately treated, following the national treatment guideline. DBS samples will be collected, processed and stored until analysis following the World Wide Antimalarial Resistance (WWARN) Molecular Testing for Malaria Standard Operating Procedures DBS Sample Collection and Transportation (http://www.wwarn.org/learning/procedures/dbs-sample-collection-andtransportation).

The prevalence of secondary malaria cases (number positive /number tested), by cRDT and hsRDT will be compared, using PCR as gold standard. Using simple analysis of performance characteristics, the sensitivity and specificity of hsRDT will be estimated in the study population. Potential correlation between the detection rate by cRDT, hsRDT and PCR will be assessed.

# 5.2. Study Period

The study will be conducted from June, 2017 to May, 2018, after obtaining administrative and ethical approval from appropriate authorities.

# 5.3. Study Area

The proposed study will be conducted in the village tract of Sakhanmaw, in Ann township in South Rakhine State. This village tract encompasses 63 villages located in a hilly forested area

with small rivers and valleys, with a total population of about 23,000 residents. Sakhanmaw village tract is covered by one rural health center (RHC) and seven sub-Centers. In addition to basic health services, malaria volunteers conduct malaria case detection and management in 52 villages. The volunteers are trained by National Malaria Control Program, University of Research Cooperation and Myanmar Medical Association.

Of the 63 villages, the research study will be carried out in about 35 villages with low malaria transmission with an annual parasite incidence (API) less than 5 per 1,000 population at risk. Based on the epidemiological data collected during 2016, the test positivity rate in the study villages ranged from 0% to 13%, and more than 80% of the malaria infections were caused by *P. falciparum*. The primary malaria vectors are *Anopheles minimus* and *An. dirus*.

#### 5.4. Study population

All adult and children at least 5 years old in the study villages under Sakhamaw RHC will be recruited and enrolled in the study.

#### **Inclusion criteria**

- Age at least 5 years old
- Resident of the villages, or temporary visitors, or co-workers or co-travelers of the index case
- Willingness to participate in the study evident by informed consent

#### **Exclusion criteria**

- Presence of severe clinical illness including severe malaria
- Non-resident index cases
- Refusal to participate in the study

Initial meetings will be organized with all partners involved in the research (NMCP, VBDC Rakhine, DMR, Defeat Malaria partners, local authorities and community leaders) to clarify the scope of the study, and prompt their active collaboration.

Additionally, specific information and sensitization activities will be organized for the communities involved in the study to explain the nature of the research, address possible concerns, and encourage their motivated participation.

